8.3.1.4. Analysis of the change in C&A-GTS-QOL ADL subscale

The change in the C&A-GTS-QOL ADL subscale score from baseline to week 8 (6th and 7th secondary endpoints) will be analyzed in the same fashion as the primary analysis in Section 8.2.1, with the exception that the baseline value of the given endpoint will be included as the covariate.

8.3.2. Sensitivity Analysis

[REDACTED]

This document is confidential.

[Redacted]

- [Redacted]

- [Redacted]

[Redacted]

#### 8.4. Exploratory Endpoints and Analysis

Exploratory endpoints for this study are as follows:

- [Redacted]
- [Redacted]
- [Redacted]
- [Redacted]
- [Redacted]
- [Redacted]
- [Redacted]
- [Redacted]
- [Redacted]
- [Redacted]
- [Redacted]
- [Redacted]
- [Redacted]
- [Redacted]
- [Redacted]

This document is confidential.

**Statistical Analysis Plan for Interventional Studies**

Sponsor: Teva Branded Pharmaceutical Products R&D, Inc./Nuvelution TS Pharma, INC.;  
Protocol No.: TV50717-CNS-30060

---

[Redacted]

8.4.1. [Redacted]

[Redacted]

8.4.2. [Redacted]

[Redacted]

[Redacted]

[Redacted]

[Redacted]

[Redacted]

8.4.3. [Redacted]

[Redacted]

[Redacted]

This document is confidential.

## **9. Safety**

The safety endpoints for this study are as follows:

- Incidence of adverse events
- Observed values and changes from baseline in vital signs
- Observed values and change from baseline in the Children's Depression Inventory, Second Edition (CDI-2), Parent and Self-report Profiles
- Observed values in the Children's Columbia-Suicide Severity Rating Scale (C-SSRS)
- Observed values in electrocardiogram (ECG) parameters and shifts from screening for clinically significant abnormal findings
- Observed values and changes from screening in clinical laboratory parameters (hematology, chemistry, and urinalysis)

The safety analysis set will be used for all safety analyses. Summaries will be presented by treatment group and for all patients.

### **9.1. Extent of Exposure**

Duration of exposure to study drug (days) for individual patients is the number of days patient received drug (last day of study drug – first day of study drug + 1). Duration of treatment (days) will be summarized using descriptive statistics. Weeks on treatment using the categories  $\leq 2$  weeks,  $>2$  to  $\leq 4$  weeks,  $>4$  to  $\leq 6$  weeks,  $>6$  to  $\leq 8$  weeks, and  $>8$  weeks will also be summarized using descriptive statistics.

### **9.2. Treatment Compliance**

Study drug administration will be included in the CRF. In the form, med ID (ID for blister pack), week range, dosing start and stop date, and number of pills taken from the blister pack are collected. Treatment compliance (%) is calculated as  $100 \times (\text{total number of pills taken} / \text{number of tablets expected to be used})$ . The total number of pills taken is the sum of pills taken from all bottles dispensed, identified by med ID. If a patient does not return a pill bottle, it will be assumed that the patient took no study drug from that bottle for the purposes of calculating compliance. The number of pills expected to be used is based on the number of morning and evening dosing times during the treatment period (2 pills are used for each dosing time point). A patient will be deemed compliant over the treatment period if the patient has taken 80% to 105% of the expected tablets of study drug.

Treatment compliance (%) will be summarized as continuous data using descriptive statistics. In addition, treatment compliance will be summarized as categorical data using descriptive statistics for the following categories:  $<80\%$ ,  $80\%$  to  $105\%$ ,  $>105\%$ .

### **9.3. Concomitant Medication**

A concomitant medication is 1) any medication that starts prior to first day of study drug administration and continues into treatment period; or 2) any medication that starts on or after the first dose of IMP and before the last dose of IMP. Concomitant medication will be summarized separately for 1) and 2). In the

This document is confidential.

case of completely missing stop date and medication is not ongoing, medication will be assumed to be concomitant. Medication cannot be considered as both prior and concomitant.

Concomitant medication summaries based on ATC level 3 and the preferred drug names will be produced for the safety analysis set. The summaries will present, by treatment group, the frequency and percentage of patients who used any medication in an ATC class, or any medication based on a single preferred drug name. Medication summaries will be sorted by descending total frequency of ATC class and by PT within ATC class. Patients will be counted only once for each medication class and each preferred drug name.

In addition, ADHD and antidepressant (see Section 7.4.1 for ATC code list) change will be summarized for:

- Proportion of patients requiring new medication;
- Proportion of patients requiring increased medication;
- Proportion of patients requiring decreased medication;
- Proportion of patients discontinued medication;
- Proportion of patients with medication switch.

#### **9.4. Adverse Events**

Adverse events will be collected and recorded from the time a patient signs the informed consent to the end of follow-up period. For this study, the follow-up period for recording of adverse events is defined as 1 week of washout for patients who will participate in the open-label safety extension study TV50717-CNS-30047 and 2 weeks after the last dose of IMP for patients who will not roll over into Study TV50717-CNS-30047.

For all AEs, preferred AE terms and system organ class (SOC) will be coded using terminology from the Medical Dictionary for Regulatory Activities (MedDRA), version 20.1 or higher.

A treatment emergent adverse event (TEAE) is defined as an AE that begins after the first administration of study medication or existing AEs that worsen after the first dose of study medication. All reported AEs will be listed, but only TEAEs will be summarized in tables.

Drug related AEs will be considered those to be reasonable possibility based on the investigators assessment. Missing relationship will considered as "Related".

Unless otherwise specified, AEs will be summarized by SOC and PT, with SOCs and PTs within SOCs presented in descending order of patient incidence.

AE summary tables are listed below:

- An overall summary of the number and percentage of patients reporting any TEAEs, serious TEAEs, treatment-related TEAEs, serious treatment-related TEAE, any TEAEs leading to study drug discontinuation, any TEAEs leading to patient study drug interruption, and TEAEs leading to death. The overall summary will also be prepared by age group (6-11 years, or 12-16 years);
- TEAEs overall and by SOC and PT;
- TEAEs by severity, overall and by SOC and PT. Missing severity, if any, will be assumed as "severe";
- Serious TEAEs, overall and by SOC and PT;

This document is confidential.

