Prohibited drugs will remain the same during the washout period for patients who will participate in the open-label extension Study TV50717-CNS-30047. Patients who will not participate in the extension study may begin/resume tic therapy medication after the first week of the washout period.

[figure not shown]
The study duration will be approximately 17 months from January 2018.

The study schematic diagram is presented in [Figure 1](#).

Figure 1: Overall Study Schematic Diagram

1:1:1 Randomization TEV-50717 high; TEV-50717 low; Placebo
N=150, 50 per treatment arm

[figure not shown]
^a If a stable dose is reached before the indicated time, the patient should continue taking that dose for the remainder of the escalation period and throughout the maintenance period. See [Table 1](#) for the maximum dose of IMP and escalation by CYP impairment status, week, and baseline body weight category.

^b This is a telephone contact for safety evaluation, required only for patients who will not participate in the open-label safety extension study for TEV-50717.

^c Ranges account for different dosing schedules for patients with baseline weight ≥ 40 kg; ≥ 40 kg, CYP impaired; 30 to < 40 kg; 30 to < 40 kg, CYP impaired; 20 to < 30 kg; and 20 to < 30 kg, CYP impaired. See [Table 1](#) for daily dose by category.

CYP=cytochrome P4502D6; CYP impaired=patients who are receiving a strong CYP2D6 inhibitor or who are a CYP2D6 poor metabolizer; ET=early termination visit.

Note: An unscheduled visit will require a clinic visit.

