The reason for and date of withdrawal from the study must be recorded on the source documentation and transcribed onto the CRF. If a patient withdraws consent, every attempt will be made to determine the reason. If the reason for withdrawal is an adverse event or a potentially clinically significant abnormal laboratory test result, monitoring will be continued at the discretion of the investigator (eg, until the event has resolved or stabilized, until the patient is referred to the care of a health care professional, or until a determination of a cause unrelated to the IMP or study procedure is made). The specific event or test result must be recorded on the source documentation and transcribed onto the CRF.

All patients who discontinue early will have a follow-up telephone contact for safety evaluation 2 weeks after their last dose of IMP ([Appendix B](#)).

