**Statistical Analysis Plan for Interventional Studies**

Sponsor: Teva Branded Pharmaceutical Products R&D, Inc./Nuvelution TS Pharma, INC.;  
 Protocol No.: TV50717-CNS-30060

- If 2 records are equidistant from the scheduled day, then the later record will be selected.
- If a patient has no scheduled record or early termination/unscheduled visits in an analysis window, the patient will be considered missing at that visit.

For these analyses performed by time period, e.g. adverse events, the following definitions will be used:

- Escalation Period - from the first dose of treatment until the day before the week 4 visit. For patients discontinued before the week 4 visit, the Escalation Period is until the later of the last dose of treatment and the early termination visit.
- Maintenance Period - from the day of the week 4 visit until the day of the week 8 visit. If a patient enters the Maintenance Period but discontinues treatment early, the Maintenance Period is until the later of the last dose of treatment and the early termination visit.
- Follow-up Period - from the end of the Maintenance Period through the end of the study.
- Overall Period - includes the Escalation Period, the Maintenance Periods, and the Follow-up Period, if applicable.

If the AE onset date is partial and can be potentially counted in multiple periods, AE will be included with the earliest period.

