## Statistical Analysis Plan for Interventional Studies

Sponsor: Teva Branded Pharmaceutical Products R&D, Inc./Nuvelution TS Pharma, INC.;  
Protocol No.: TV50717-CNS-30060

---

- Serious treatment-related TEAEs, overall and by SOC and PT ;
- TEAEs by relationship to study treatment, overall and by SOC and PT;
- TEAEs leading to study drug discontinuation, overall and by SOC and PT;
- TEAEs leading to study drug interruption, overall and by SOC and PT;
- TEAEs leading to dose reduction overall and by SOC and PT;
- Most common TEAEs, overall and by PT. Most common TEAEs are defined as TEAEs that occur in > 4% of the patients in either of the treatment groups. ;
- SMQs for suicide/self-injury, depression (exclude suicide and self-injury), and Parkinson-like events.

For summary tables, patients having more than 1 event with the same PT will be counted once for that term. Patients having more than 1 event with the same SOC will be counted once for each event and once for that SOC. For tabulations by severity, only a patient's most severe event within the category (e.g. overall, SOC, PT) will be counted; similarly, for tabulations by relationship, only a patient's most related event within a category will be counted. Summaries will be presented by treatment group and for all patients. The denominator for percentages will be the number of patients in safety analysis set for the given treatment group (i.e., the N's for the columns). Summary of all TEAEs will be presented in the overall period (escalation plus maintenance phase plus follow-up period) and for the escalation period, maintenance period, and follow-up period. By period summary will be based on the period the AE occurred (Section 6.4). Same type of AE may be counted in multiple periods in cases below:

- AE resolved in the same period and reoccurred in a new period.
- AE increased severity in another period.

Same AE will be counted only once in summary in the overall period.

All adverse events in the overall treatment period will be summarized by CYP2D6 impairment status (Impaired/Not impaired). In addition, serious AEs and AEs by severity will be summarized by CYP2D6 impairment status.

Listings will be provided for all AEs and the following subsets:

- All AEs
- Serious AEs
- AEs leading to study drug discontinuation
- AE leading to dose interruption
- AEs leading to death.

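### The Follow-up Period AE table pools 7-day and 14-day post-dose windows, and its second week can include events that arise after other tic drugs are started

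*SAP*

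**What the plan says.** - **Start, no stop.** SAP 9.4: "A treatment emergent adverse event (TEAE) is defined as an AE that begins after the first administration of study medication". Worsening of an existing event also counts. The definition names no last day.
- **Two collection windows.** SAP 9.4 collects AEs for "1 week of washout for patients who will participate in the open-label safety extension study TV50717-CNS-30047", but until "2 weeks after the last dose of IMP for patients who will not roll over into Study TV50717-CNS-30047". Protocol 7.1.2 agrees.
- **Early terminators are in the longer window.** Protocol 4.3: "All patients who discontinue early will have a follow-up telephone contact for safety evaluation 2 weeks after their last dose of IMP". Only patients who complete the study may enter the extension (Protocol 3.1, SAP 3.4).
- **One follow-up period.** SAP 6.4: "Follow-up Period - from the end of the Maintenance Period through the end of the study". SAP 9.4 tabulates TEAEs for this period and also includes it in the overall period. Percentages use the arm's safety-set count, with no adjustment for time observed.
- **Other tic drugs.** Protocol 3.1: "Patients who will not participate in the extension study may begin/resume tic therapy medication after the first week of the washout period". The note under Table 9 in Protocol Appendix H lifts the antipsychotic prohibition for these patients at the same point.

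**The concern.** Whether a patient is watched for 7 or 14 days after the last dose depends on completing the study and choosing to roll over. Both happen after randomization, and both can depend on tolerability or response. A crude percentage over the safety-set count does not allow for this. Two patients with the same risk are not equally likely to appear in the follow-up table, and if the mix differs by arm, so does the expected percentage.

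The second problem needs no assumption about roll-over rates. The extra week is the one in which a non-rollover may already be taking a different tic drug. An event caused by that drug meets the TEAE definition and is credited to TEV-50717 or placebo. The follow-up table is the only AE table for the off-drug period, so a reader looking for withdrawal effects would be reading a mixture.

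**Working it through.** **1. The plan's own days.** Treatment ends on day 56. 56 + 7 = 63 and 56 + 14 = 70, which match the week 9 visit and week 10 call in Protocol Table 2. Per patient, the post-dose ratio is 14/7 = 2.0 and the total ratio is 70/63 = 1.11. These are nominal, since visits carry a 3-day window.

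**2. Effect of roll-over alone, in completers.** The documents give no roll-over shares or weekly AE risks, so both are assumed. Let *r* be the share rolling over and *w* a constant weekly risk of a first event, equal in both arms.

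- Follow-up % = r·w + (1 − r)·[1 − (1 − w)²]. The between-arm difference is (r₁ − r₂)·w·(1 − w).
- Overall % = r·[1 − (1 − w)⁹] + (1 − r)·[1 − (1 − w)¹⁰]. The difference is (r₁ − r₂)·w·(1 − w)⁹.

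For w from 2% to 10%:

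| Roll-over, two arms | Mean post-dose days | Follow-up table, false difference (points) | Overall table, false difference (points) |
|---|---|---|---|
| 90% / 90% | 7.70 / 7.70 | 0 | 0 |
| 95% / 85% | 7.35 / 8.05 | 0.20 to 0.90 | 0.17 to 0.39 |
| 90% / 70% | 7.70 / 9.10 | 0.39 to 1.80 | 0.33 to 0.77 |
| 95% / 50% | 7.35 / 10.50 | 0.88 to 4.05 | 0.75 to 1.74 |
| 100% / 0% | 7.00 / 14.00 | 1.96 to 9.00 | 1.67 to 3.87 |

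With about 50 patients per arm, one patient is 1/50 = 2 points. The last row is a bound, not an expectation. Extra events from new tic drugs are not modelled.

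**3. Early termination and the overall table.** Early terminators have a longer post-dose window but fewer days on treatment. Assume 4% terminate on placebo and 12% on high dose (mean 8%, the overall rate quoted in SAP 8.2.2), with a mean stop at day 28. Mean days observed = (1 − e)·[56 + 7r + 14(1 − r)] + e·(28 + 14):

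- Roll-over 90% / 90%: 0.96 × 63.7 + 0.04 × 42 = 62.8 on placebo; 0.88 × 63.7 + 0.12 × 42 = 61.1 on high dose.
- Roll-over 95% / 85%: 62.5 and 61.4.
- Roll-over 90% / 75%: 62.8 and 62.0.

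High dose is observed for less time in all three cases, and this holds for any mean stop before about day 38. Capping every patient at last dose + 7 gives 0.96 × 63 + 0.04 × 35 = 61.9 against 0.88 × 63 + 0.12 × 35 = 59.6. The gap widens to 2.2 days, from 0.8 to 1.7.

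**4. Early terminators in the follow-up table.** SAP 6.4 ends their Escalation or Maintenance Period at the later of last dose and the early-termination visit, and starts follow-up after Maintenance. Someone who stops in Maintenance contributes at most 14 days. Someone who stops before week 4 has no Maintenance Period, so their follow-up is undefined.

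**5. Visibility of a new tic drug.** SAP 7.4.1 counts a drug as prior if it stopped before the first dosing day. SAP 9.3 counts it as concomitant if it was already running and continued into treatment, or if it started before the last dose. A drug started after the last dose is in neither summary, although Protocol 5.6 records it on the CRF through follow-up.

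**The case against.** Much of the opposing case stands. Roll-over and early-termination rates by arm are assumptions. Escalation and Maintenance TEAE tables are specified separately and do not depend on roll-over. AE tables are descriptive, events are also tabulated by relationship, all AEs are listed, and later drugs are on the CRF, so an individual event can be traced. Tic drugs are permitted in the second week, not required. In a paediatric trial that monitors depression and suicidality, keeping every collected event in the main tables is a defensible conservative choice.

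A reader might infer four stronger things that the documents do not support:

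- *TEAEs are unbounded.* Collection limits non-serious events to 7 or 14 nominal days. The exception is a late-reported serious event (Protocol 7.1.2), which the open definition and the inclusion of all data to database lock (SAP 2.2) could admit.
- *The overall TEAE table is biased against high dose.* Step 3 shows that the direction can reverse, and that a cap on every table can widen the gap in observation time.
- *Follow-up percentages rise even with equal roll-over, because early terminators add 14 days.* At 90% roll-over in both arms and 4% against 12% termination, mean post-dose collection is 7.95 and 8.46 days (+6%). SAP 6.4 does not place all of those days in the Follow-up Period.
- *The follow-up AE table is the only view of withdrawal.* Week 9 also has vital signs, CDI-2, C-SSRS and summarized efficacy scales.

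None of this gives the follow-up table a common window or separates events that arise after a new tic drug.

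**Conclusion.** The point holds for the Follow-up Period table. The 7-against-14-day difference between patients, the pooling over safety-set counts and the possible inclusion of other tic drugs' events all follow from the text. A difference between arms does not; it needs roll-over or early termination to differ by arm. Under the assumed constant and equal risks, a 20-point gap in roll-over produces a false follow-up difference of 0.4 to 1.8 points, less than one patient in 50. A 45-point gap produces 0.9 to 4.05 points, up to about two patients. The effect on the overall TEAE table is probably small (0.3 to 0.8 points at 90% against 70%) and its direction is not fixed. The case for change is that the follow-up table becomes interpretable at little cost, not that a large bias has been shown.

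**What to change.** Before unblinding, amend SAP 6.4 and 9.4:

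1. Define the comparative Follow-up Period table as onset or worsening after the end of treatment through 7 days after the patient's last dose, for every patient, including those who stop before week 4. State where an event between the last dose and a later early-termination visit is counted, since SAP 6.4 now assigns it to Escalation or Maintenance.
2. Show later events (days 8 to 14 and any late-reported serious events) in a separate column or table, with any tic drug started after the last dose.
3. Keep the overall TEAE, serious-AE and suicidality tables on all collected events.
4. Add one overall TEAE summary limited to first dose through last dose + 7 days. It equalizes the post-dose window only, not time on treatment.

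The cost is one date flag, one or two extra tables, and slightly fewer events in the follow-up table. Collection, treatment and patient management do not change.

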## Statistical Analysis Plan for Interventional Studies

Sponsor: Teva Branded Pharmaceutical Products R&D, Inc./Nuvelution TS Pharma, INC.;  
Protocol No.: TV50717-CNS-30060

---

- Serious treatment-related TEAEs, overall and by SOC and PT ;
- TEAEs by relationship to study treatment, overall and by SOC and PT;
- TEAEs leading to study drug discontinuation, overall and by SOC and PT;
- TEAEs leading to study drug interruption, overall and by SOC and PT;
- TEAEs leading to dose reduction overall and by SOC and PT;
- Most common TEAEs, overall and by PT. Most common TEAEs are defined as TEAEs that occur in > 4% of the patients in either of the treatment groups. ;
- SMQs for suicide/self-injury, depression (exclude suicide and self-injury), and Parkinson-like events.

For summary tables, patients having more than 1 event with the same PT will be counted once for that term. Patients having more than 1 event with the same SOC will be counted once for each event and once for that SOC. For tabulations by severity, only a patient's most severe event within the category (e.g. overall, SOC, PT) will be counted; similarly, for tabulations by relationship, only a patient's most related event within a category will be counted. Summaries will be presented by treatment group and for all patients. The denominator for percentages will be the number of patients in safety analysis set for the given treatment group (i.e., the N's for the columns). Summary of all TEAEs will be presented in the overall period (escalation plus maintenance phase plus follow-up period) and for the escalation period, maintenance period, and follow-up period. By period summary will be based on the period the AE occurred (Section 6.4). Same type of AE may be counted in multiple periods in cases below:

- AE resolved in the same period and reoccurred in a new period.
- AE increased severity in another period.

Same AE will be counted only once in summary in the overall period.

All adverse events in the overall treatment period will be summarized by CYP2D6 impairment status (Impaired/Not impaired). In addition, serious AEs and AEs by severity will be summarized by CYP2D6 impairment status.

Listings will be provided for all AEs and the following subsets:

- All AEs
- Serious AEs
- AEs leading to study drug discontinuation
- AE leading to dose interruption
- AEs leading to death.

